4.6.3 Methods for Unblinding

4.6.3.1 Unblinding in the Event of a Medical Emergency

In the event of a medical emergency, the investigator may unblind an individual subject's investigational product allocation. Instructions for unblinding an individual subject's investigational product allocation are contained in the IXRS manual. In general, unblinding should only occur if management of the medical emergency would be different based on the subject having received investigational product. In the majority of cases, the management of a medical emergency would be the same whether or not investigational product was received by the subject. If this was the case, the investigational product allocation should not be unblinded.

MedImmune retains the right to unblind the treatment allocation for SAEs that are unexpected and are suspected to be causally related to an investigational product and that potentially require expedited reporting to regulatory authorities.

If a subject's investigational product allocation is unblinded, the subject should be discontinued from investigational product.

4.6.3.2 Unblinding for PK [REDACTED] Analysis

A small number of clinical bioanalytical personnel, who will not be involved in the treatment or clinical evaluation of subjects, will be unblinded to subject treatment allocation to analyze PK and immunogenicity samples. Local SOPs will govern maintenance of the blind and information on treatment allocation will not be communicated outside of these clinical bioanalytical personnel.

4.7 Restrictions During the Study and Concomitant Treatment(s)

The investigator must be informed as soon as possible about any medication taken from the time of screening until the end of the study (end-of-study visit). Any concomitant medication(s), including herbal preparations, taken during the study will be recorded in the eCRF.

4.7.1 Permitted Concomitant Medications

Investigators may prescribe concomitant medications or treatments deemed necessary to provide adequate supportive care, except for those medications identified as “excluded” and listed in Section 4.7.2. Specifically, subjects should receive full supportive care during the study, including transfusions of blood and blood products, and treatment with antibiotics, antiemetics, antidiarrheals, analgesics, and other care as deemed appropriate and in accordance with their institutional guidelines.

4.7.2 Prohibited Concomitant Medications

Other than the medications described above, use of concomitant medications including OTC medications, herbal supplements, vitamins, etc at the times specified in the list below is not permitted. Subjects must be instructed not to take any medications including OTC products without first consulting with the investigator.

Use of the following concomitant medications is not permitted:

- Concurrent use of SGLT2 inhibitors (except for dapagliflozin), GLP-1-analogue-containing preparation or any other glucose-lowering agent other than metformin within the last 30 days or 5 half-lives of the drug (whichever is longer) at the time of screening (Visit 1)
- Concurrent use of any medicinal products, or herbal or OTC preparations licensed for control of body weight or appetite at the time of screening (Visit 1)
- Concurrent or previous use of drugs approved for weight loss (eg, orlistat, bupropion-naltrexone, phentermine-topiramate, phentermine, lorcaserin) within the last 30 days or 5 half-lives of the drug, whichever is longest, at the time of screening. (Visit 1)
- Any other investigational agent not included in the protocol within last 30 days or 5 half-lives (whichever is longer) from screening (Visit 1)
- Concurrent use of Aspirin (acetylsalicylic acid) at a dose greater than 150 mg once daily and within the last 72 hours prior to the start of the study (Visit 4)
- Concurrent use of paracetamol (acetaminophen) or paracetamol-containing preparations at a total daily dose of greater than 3000 mg once daily and within the last 72 hours prior to the start of the study (Visit 4)

- Concurrent use of ascorbic acid (vitamin C) supplements at a total daily dose of >than 1000 mg and within the last 72 hours prior to the start of the study (Visit 4)
- Concurrent use of opiates, domperidone, metoclopramide, or other drugs known to alter gastric emptying and within the last 72 hours prior to the start of the study (Visit 4)
- Loop diuretics within one month prior to screening (Visit 1) and during the study

4.8 Statistical Evaluation

4.8.1 General Considerations

Data will be provided in listings sorted by treatment group and subject number. Tabular summaries will be presented by treatment group. Categorical data will be summarized by the number and percentage of subjects in each category. Continuous variables will be summarized by descriptive statistics, including mean, standard deviation (SD), median, minimum, and maximum. Baseline values will be defined as the last valid assessment prior to the first administration of investigational product unless otherwise specified. Details of endpoint analyses will be described in the statistical analysis plan.

4.8.1.1 Analysis Population

Efficacy Population: The Intent-to-treat (ITT) population includes all subjects who are randomized and receive any investigation product analyzed according to their randomized treatment group.

Safety Population: The As-treated population includes all subjects who receive any investigation product analyzed according to the treatment they actually receive.

PK Population: The PK population includes all subjects who received at least 1 dose of investigational product and had at least one PK sample taken that is above the lower limit of quantitation.

[REDACTED]

4.8.2 Sample Size and Power Calculations

A total of 46 subjects are planned for the study. Each of the 2 treatment groups will be randomized at a 1:1 ratio to receive (a) MEDI0382 with dapagliflozin and metformin administered simultaneously or (b) placebo with dapagliflozin and metformin administered simultaneously. A sample size of 23 subjects in each treatment group will provide a study

power > 95% to detect a difference of 30% between treatment groups in relative change from baseline in glucose AUC_{0-4h} at a two-sided alpha of 5%, assuming a common SD of 20%.

This sample size will also provide a study power > 95% to detect a difference of 225 hr•mg/dL between treatment groups in absolute change from baseline in glucose AUC_{0-4h} at a two-sided alpha of 5%, assuming a common SD of 150 hr•mg/dL. The SD assumptions are based the result of 300 µg cohorts in a prior study (D5670C00002).

4.8.3 Efficacy

4.8.3.1 Primary Efficacy Analysis

The primary efficacy analysis will be based on the ITT population. The primary endpoints, change and % change from baseline to the end of 28 days of treatment in glucose AUC_{0-4h} as measured by a MMTT, will be summarized by treatment group. Statistical comparisons of these endpoints between MEDI0382/dapagliflozin/metformin and placebo/dapagliflozin/metformin treatment groups will be performed using an analysis of covariance by adjusting baseline and treatment group with last-observation-carried-forward (LOCF) approach to handle missing data.

Descriptive statistics at each time point will be provided by treatment group.

4.8.3.2 Secondary Efficacy Analyses

Secondary efficacy and pharmacodynamics (PD) analysis will be based on the ITT population. The following endpoints will be summarized by treatment group and analyzed similarly to the analysis of primary efficacy endpoints.

- Change from baseline to the end of dosing at each dose level (Days 7, 14, and 28) in glucose AUC at 24 hours as measured by CGM
- Change from baseline to the end of dosing at each dose level (Days 7, 14, and 28) in 24-hour mean glucose as measured by CGM
- Change from baseline to the end of dosing at each dose level (Days 7, 14, and 28) in SD of 24-hour glucose readings as measured by CGM
- Change from baseline to Days 7, 14, and 28 in coefficient of variation (ratio of SD:mean over 24 hours) of glucose readings as measured by CGM
- Change from baseline to Days 7, 14, and 28 in the mean amplitude of glucose excursion of 24-hour glucose readings as measured by CGM
- Change from baseline to Days 7, 14, and 28 in the % of 24-hour glucose readings obtained from CGM that fall within the euglycemic range of ≥ 70 mg/dL (≥ 3.9 mmol/L) and ≤ 180 mg/dL (≤ 10.0 mmol/L)

- Change from baseline to Days 7, 14, and 28 in the % of 24-hour glucose readings obtained from CGM that fall within the hyperglycemic range of > 180 mg/dL (> 10 mmol/L)
- Change from baseline to Days 7, 14, and 28 in the % of 24-hour glucose readings obtained from CGM that fall within the hypoglycemic range of < 70 mg/dL (< 3.9 mmol/L)
- Change from baseline to Days 7, 14, and 28 in the % of 24-hour glucose readings obtained from CGM that fall within the clinically significant hypoglycemic range of < 54 mg/dL (< 3.0 mmol/L)

Descriptive statistics at each time point will be provided by treatment group.

4.8.3.3 Exploratory Analyses

Exploratory efficacy and PD analysis will be based on the ITT population. The following endpoints will be summarized by treatment group and analyzed similarly to the analysis of primary efficacy endpoints.

- Change from baseline (Day -1) to Day 28 in FPG
- Change from baseline (Day -2) to Day 28 in HbA1c
- Change from baseline (Day -1) to Day 28 in active GLP-1, glucagon, insulin, c-peptide AUC_{0-4h} as measured by MMTT
- Change from baseline (Day -1) to Day 7, 14, and 28 in fasting FFA level
- Change from baseline (Day 1) to Day 29 in body weight (kg)
- Percentage change from baseline (Day 1) to Day 29 in body weight (kg)
- Total glucose excreted in urine collected for 24 hours

For the proportion of subjects achieving $\geq 5\%$ body weight loss from baseline after 28 days treatment, pairwise statistical comparisons between MEDI0382/dapagliflozin/metformin and placebo/dapagliflozin/metformin treatment groups will be made using a logistic regression by adjusting baseline and treatment group with an LOCF approach to handle missing data.

Descriptive statistics at each time point will be provided by treatment group.

4.8.4 Safety

4.8.4.1 Analysis of Adverse Events

Safety analysis will be based on the As-treated population. Adverse event collection begins after the subject signs the ICF and lasts until the end of the study. Treatment-emergent AEs

(TEAEs) and treatment-emergent SAEs (TESAEs) will be coded by the most updated version of the Medical Dictionary for Regulatory Activities (MedDRA), and the type, incidence, severity and relationship to investigational product will be summarized by MedDRA's System Organ Class, Preferred Term, and by treatment group. Treatment-emergent AEs leading to discontinuation, TEAEs leading to death, and deaths will also be summarized. Specific TEAEs will be counted once for each subject for the calculation of percentages. In addition, if the same TEAE occurs multiple times within a particular subject, the highest severity and level of relationship observed will be reported.

4.8.4.2 Analysis of Safety Data

Safety data such as vital signs (including 24-hour ABPM) will be summarized by treatment group at each time point. Change from baseline to each postbaseline time point in these data will also be summarized, where appropriate. Electrocardiogram parameters will also be assessed and summarized descriptively by treatment group.

4.8.4.3 Analysis of Clinical Laboratory Parameters

Clinical laboratory data will be summarized by treatment group at each time point. Change from baseline to each postbaseline time point in these data will also be summarized, where appropriate.

4.8.5 Analysis of [REDACTED] Pharmacokinetics

4.8.5.1 Pharmacokinetic Analyses

If data allow, PK parameters such as C_{max} , t_{max} , AUC, and terminal elimination half-life will be estimated from plasma concentration-time data for MEDI0382 and β -hydroxybutyrate at each dose level separately and for 10 mg dapagliflozin. Moreover, if data allow, additional parameters such as apparent clearance may be derived for MEDI0382 at all dose levels and for 10 mg dapagliflozin.

Descriptive statistics will be generated for PK parameters for the MEDI0382 and dapagliflozin group in each cohort. Subjects who have at least one measurable concentration time point of investigational product will be used for this analysis.

[REDACTED]

[REDACTED]

[REDACTED]

[REDACTED]

[REDACTED]

4.8.6 Interim Analysis

No interim analysis is planned.

5 ASSESSMENT OF SAFETY

5.1 Definition of Adverse Events

The ICH Guideline for GCP E6(R1) defines an AE as:

Any untoward medical occurrence in a patient or clinical investigation subject administered a pharmaceutical product and which does not necessarily have a causal relationship with this treatment. An AE can therefore be any unfavorable and unintended sign (including an abnormal laboratory finding), symptom, or disease temporally associated with the use of a medicinal product, whether or not considered related to the medicinal product.

An AE includes but is not limited to any clinically significant worsening of a subject's pre-existing condition. An abnormal laboratory finding (including ECG finding) that requires medical intervention by the investigator, or a finding judged by the investigator as medically significant should be reported as an AE. If clinical sequelae are associated with a laboratory abnormality, the diagnosis or medical condition should be reported (eg, renal failure, hematuria) not the laboratory abnormality (eg, elevated creatinine, urine red blood cell count increased). Abnormal laboratory values that are not, in the investigator's opinion, medically significant and do not require intervention should not be reported as AEs.

Adverse events may be treatment emergent (ie, occurring after initial receipt of investigational product) or non-treatment emergent. A non-TEAE is any new sign or symptom, disease, or other untoward medical event that begins after written informed consent has been obtained but before the subject has received investigational product.

Elective treatment or surgery or preplanned treatment or surgery that was scheduled prior to the subject being enrolled into the study for a documented preexisting condition that did not worsen from baseline is not considered an AE (serious or nonserious). An untoward medical event occurring during the prescheduled elective procedure or routinely scheduled treatment should be recorded as an AE or SAE.

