1.6.3 Volume Depletion

MEDI0382 treatment with doses of up to 300 µg has been associated with a reduction in BP compared to baseline (-2.26 mmHg for diastolic BP and -8.49 mmHg for systolic BP) as estimated by ambulatory blood pressure monitoring (ABPM).

GLP-1 receptor agonist augment renal sodium excretion ([Tonnejck et al, 2016](#)). The mechanism by which a GLP-1 receptor agonist increase renal excretion is not well understood, but it includes vasodilation and possibly a direct effect on the renal tubule. ([DeFronzo, 2017](#)).

Dapagliflozin causes glucosuria and a subsequent mild osmotic diuretic effect and decreased intravascular volume. Due to its mechanism of action, dapagliflozin increases diuresis associated with a modest decrease in BP, which could be more pronounced in patients with very high blood glucose concentrations. Refer to the current dapagliflozin IB for more information on this risk.

The combined sodium loss and the potential tolerability risk (vomiting) resulting from GLP-1 on a background of dapagliflozin raises a theoretical risk of higher incidence of symptomatic hypovolemia in subjects given both products in combination.

During the course of this study, the subject volume status will be closely monitored at each visit by assessing vital signs with BP (including lying and standing measurements). In addition, an ABPM device will be used during inpatient and outpatient visits.

Subjects will be advised to maintain adequate fluid intake throughout the study and to contact the study team if they experience dizziness or feel unwell. Management of volume depletion events should be as per standard local protocols.

Any episodes of symptomatic volume depletion (eg, hypotension, dehydration, or syncope) should be recorded as an AE.

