### 3.6 Safety Analyses

#### 3.6.1 Adverse Events and Serious Adverse Events

Adverse events (AE) will be coded by MedDRA version 20.0 or higher. Analysis of adverse events will include the type, incidence, severity and relationship to study investigational product (MEDI0382 or dapagliflozin) summarized by MedDRA System Organ Class (SOC) and Preferred Term by treatment group as well as for overall treatments. The AEs summaries will include only treatment-emergent AEs; ie, those occurring after initial receipt of investigational product. Subjects will be counted once for specific PT or MedDRA SOC when calculating incidence. If the same AE Preferred Term occurs multiple times within a subject, the highest severity and level of relationship observed will be reported. Non-treatment-emergent AEs/serious adverse events will be presented in the listings.

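### Treatment emergence is defined by timing alone, with no clause for worsening, so an AE recorded before the first SC dose that worsens afterwards may be left out of the TEAE tables

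*Protocol*

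**What the plan says.** Protocol 5.1 sorts adverse events by timing: "Adverse events may be treatment emergent (ie, occurring after initial receipt of investigational product) or non-treatment emergent". It then describes the second class: "A non-TEAE is any new sign or symptom, disease, or other untoward medical event that begins after written informed consent has been obtained", as long as this is before investigational product. There is no exception for an event that later gets worse.

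SAP 3.6.1 carries the rule into the analysis: "The AEs summaries will include only treatment-emergent AEs; ie, those occurring after initial receipt of investigational product". The remainder are listed only: "Non-treatment-emergent AEs/serious adverse events will be presented in the listings".

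Protocol 5.1 does mention worsening, but in the general definition of an AE: "An AE includes but is not limited to any clinically significant worsening of a" condition that the subject already had.

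On when recording starts, Protocol 4.8.4.1 says: "Adverse event collection begins after the subject signs the ICF and lasts until the end of the study". Protocol 5.4.1 starts collection at admission on Day -2. The run-in schedule (Table 4.2.2-1) has AE assessments on Days -28 and -14.

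**The concern.** The study asks what MEDI0382 adds to dapagliflozin and metformin, and safety and tolerability is a secondary objective (Protocol Table 2.2-1). Subjects who enter on metformin alone take dapagliflozin for 28 days before randomization, so some may reach Day 1 with an ongoing complaint. Protocol 1.6.3 says that sodium loss together with vomiting, on a dapagliflozin background, "raises a theoretical risk of higher incidence of symptomatic hypovolemia in subjects given both products in combination". Such harm could appear as a new event, or as mild dizziness or nausea that becomes moderate or severe.

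A definition based only on when an event begins captures the first form and may miss the second. If the eCRF does not hold the date on which the grade rose, later programming cannot recover it.

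**Working it through.** The plan gives no figure on this point, so the check is a reading of the text. Take an invented case: grade 1 dizziness begins before Day 1, is still present at the first SC dose, and becomes grade 2 on treatment. Protocol 4.5.1.3 fixes Day 1 as the first day of MEDI0382 or placebo.

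1. **Classification.** Under Protocol 5.1 the dizziness began before dosing, so as a single record it is non-treatment-emergent. SAP 3.6.1 then lists it and does not tabulate it.

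2. **Recording a worsening.** If the site enters the grade 2 episode as a separate AE with its own start date, that record occurs after dosing and is a TEAE. Neither document asks for this. Protocol 5.4 covers a TEAE that becomes serious, which concerns seriousness rather than grade, and only events that are already TEAEs. The highest-severity rule in Protocol 4.8.4.1 is worded for TEAEs, and the one in SAP 3.6.1 operates inside TEAE-only summaries. Two sites could both follow the protocol and produce different tables.

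3. **Meaning of investigational product.**
   - Dapagliflozin is included in Protocol Table 4.5.1-1, in the relationship wording of SAP 3.6.1, and in the dapagliflozin and ketone PK rows of SAP Table 3.2-1.
   - It is excluded in the ITT and As-treated rows of SAP Table 3.2-1 and in the SAP 3.1 baseline rule, both of which specify MEDI0382 or placebo. Footnotes i and r of Protocol Table 4.2.3-1 name dapagliflozin separately from investigational product.
   - If it is included, a run-in event in a metformin-monotherapy subject is a TEAE from Day -28. Dual-therapy subjects receive study dapagliflozin only from randomization (Protocol 4.5.2). The anchor would then differ by background therapy, and pre-randomization events would enter the comparison between arms.

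4. **Start of AE collection.** Under Protocol 5.4.1, a complaint that began before Day -2 is not an AE record but a pre-existing condition. Its clinically significant worsening after Day 1 is then an AE that occurs after dosing, hence a TEAE. Under Protocol 4.8.4.1 and Table 4.2.2-1 the same complaint is already an AE on record, and step 1 applies. Even under 5.4.1, an AE that begins between Day -2 and the first dose remains exposed.

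5. **Outputs affected.** These are the TEAE incidence, severity and relationship tables. Deaths are summarized regardless (Protocol 4.8.4.1). SAP 3.6.3 does not repeat the TEAE limit for discontinuations, although Protocol 4.8.4.1 applies it. Laboratory shifts (SAP 3.6.4), vital signs and ABPM (SAP 3.6.5.1) do not depend on TEAE status.

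6. **Size.** One subject in an arm of 23 is 1/23 = 4.3 percentage points. If a subjects are missed on MEDI0382 and b on placebo in a given table row, the difference (MEDI0382 minus placebo) is understated by (a − b)/23. Illustrative values, not from the documents: a = 0, b = 0 gives 0; a = 1, b = 0 gives 4.3 points; a = 2, b = 0 gives 8.7 points; a = 1, b = 1 gives 0; a = 0, b = 1 gives −4.3 points. A subject counts as missed only if no other record already places that subject in the same row.

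**The case against.** The best counter-argument is that Protocol 5.1 already makes clinically significant worsening an AE, so a worsening after dosing is an AE that occurs after dosing and therefore a TEAE. Protocol 1.6.3 also requires any symptomatic volume-depletion episode to be recorded as an AE, which gives a post-dose episode a route into the tables. The statistical programming plan and any eCRF guidance might hold a recording rule, and neither is available here. The study is exploratory.

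Part of this stands. Exclusion is possible but not certain, and a reader who infers that every such event is lost goes beyond the text. But the documents never say that an AE already on record counts as a pre-existing condition, or that its worsening gets a new start date. The volume-depletion sentence does not say how to treat an episode already open at Day 1, and it does not cover nausea.

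A reader might also infer that events starting on newly begun dapagliflozin are the clear casualties. That is not secure, because on the wider meaning of investigational product they are already TEAEs.

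**Conclusion.** The gap is real but conditional. Neither document has a worsening clause, and on-treatment aggravation of an AE recorded before the first SC dose may be left out of the TEAE incidence, severity and relationship tables, depending on site recording practice. The inconsistent meaning of investigational product and the conflicting start of AE collection make the outcome harder to predict.

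Three stronger conclusions are tempting and not supported:

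- **That the events vanish from every safety output.** Listings, deaths, laboratory shifts and ABPM remain.
- **That the bias can only favour MEDI0382.** The rule applies to both arms, and worsening on placebo is missed too. An understated excess on MEDI0382 is the main direction only if MEDI0382 does aggravate ongoing events.
- **That the loss can be estimated from the nausea (41.7%) and vomiting (27.3%) figures in Protocol 3.2.3.2.** Those are the highest cohort incidences on MEDI0382, not probabilities that an ongoing event worsens. The documents give no prevalence of AEs ongoing at Day 1 to multiply them by.

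The size is therefore unknown. It is near zero if few AEs are ongoing at Day 1, and each net missed subject is 4.3 points.

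**What to change.** In Protocol 5.1 and SAP 3.6.1, define a TEAE as an AE that starts, or increases in severity grade, after the first SC dose of MEDI0382/placebo. Use that one anchor for TEAE status throughout, whatever investigational product means elsewhere. In the eCRF guidance, have sites record a severity increase after that dose as a new AE with its own start date and grade, on the existing Appendix 3 scale. Reconcile the start of AE collection between Protocol 4.8.4.1, Protocol 5.4.1 and Table 4.2.2-1.

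The cost is about one sentence in each document for the definition, a line of eCRF guidance and the correction of the collection dates. The downside is a few more TEAE rows and slightly more data entry.
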